6.8.3 Analyses of other measures

In addition to primary, secondary, and safety measures, the following additional outcomes will be analyzed to help with the interpretation of study results:

- Descriptive statistics for body weight, blood pressure, serum creatinine, HbA1c, and serum uric acid at each post-baseline visit and their changes from baseline, by treatment group in the ITT population. No imputation for missing data will be employed.
- Percentage of subjects receiving adequate study medication exposure (i.e., allopurinol or placebo) independent of adverse events. This is defined as the actual total dose during the 156-week dosing period, as determined from the dispensed dosage and pill counts, divided by the expected total dose defined by the eGFR-adjusted protocol-described dosing regimen, without consideration for temporary or permanent discontinuations or reductions owing to adverse events. The proportion of subjects receiving the presumed adequate study medication exposure is defined as the number of subjects who had at least 80% and no more than 120% of the intended study medications during the entire dosing period, independent of adverse events, among all randomized subjects. No imputation for missing data will be employed.

6.8.4. Analysis of the effect of post-randomization sUA changes on iGFR value at Visit 17

The analysis outlined below will be performed using linear model with correlated errors. In addition to fixed effects associated with baseline covariates, we will include fixed effects associated with visit-specific effects of another covariate, namely the average sUA change from baseline over the initial post-randomization period (Visits 6-10) on iGFR values. We note that this covariate is created based on sUA values that precede iGFR measures (our dependent variable) and in this way we attempt to mitigate the impact of the bidirectional relationship between concurrent measures of sUA and iGFR.

Analysis	Analysis of the effect of post-randomization average changes of sUA values (V6-V10) relative to sUA at baseline on iGFR value at Visit 17
Analysis Set	ITT Population
Methods	Linear model with correlated errors for longitudinal iGFR measures
Dependent Variable	iGFR measured at Visits V11 (80 weeks), V16 (156 weeks) and V17 (164 weeks after randomization)
Model	Fixed effects associated with: 
 • Visit-specific intercepts corresponding to V11, V16, V17 • Visit-specific effects of sUA change on iGFR at V11, V16, V17 • Stratifying variables: sUA, HbA1c, study center • Albuminuria status at baseline with 2 levels • Baseline AER geometric mean (at Visits 3 and 4 combined) expressed on log to base 10 scale • Baseline iGFR
Results	
 • Estimate of an effect of an average sUA changes from baseline on iGFR value at Visit 17, adjusted for stratifying variables and baseline covariates • 95% confidence interval for sUA changes effect • P-value for sUA changes effect

6.8.5. Time to 40% eGFR decrease

Analysis	Analysis of time to 40% eGFR decrease from randomization
Analysis Set	ITT Population
Methods	Proportional hazards model for interval censored data.
Dependent Variable	Time to endpoint of 40% eGFR decrease from randomization
Proportional Hazards Model	Fixed effects associated with: 
 • Stratifying variables: sUA, HbA1c, study center • Treatment group • Albuminuria status with 2 levels • Baseline AER geometric mean (at Visits 3 and 4 combined) expressed on log to base 10 scale
Results	
 • N(%) of subjects with 40% eGFR decrease during the course of the study • Hazard ratio of allopurinol to placebo • 95% confidence interval for hazard ratio • P-value for treatment effect

6.8.6. Time to doubling of serum creatinine, end-stage renal disease (ESRD), or cardiovascular/renal death

Variable of interest (endpoint) is defined as a composite of three events: (1) doubling to serum creatinine, (2) ESRD, or (3) cardiovascular/renal death. Time to event is defined as time from randomization to the first event (one of the events defined above) or censoring (lost-to-follow-up, withdrawal, death other than due to cardiovascular/renal cause, and study completion without experiencing the event).

Analysis Set	ITT Population
Methods	Proportional hazards model for interval censored data.
Dependent Variable	Time from randomization to composite endpoint of serum creatinine doubling, ESRD or cardiovascular/renal death
Proportional Hazards Model	Fixed effects associated with: 
 • Stratifying variables: sUA, HbA1c, study center • Treatment group • Albuminuria status with 2 levels • Baseline AER geometric mean (at Visits 3 and 4 combined) expressed on log to base 10 scale • Baseline iGFR
Results	
 • N(%) of subjects with doubled serum creatinine, ESRD or cardiovascular/renal death during the course of the study • Hazard ratio of allopurinol to placebo • 95% confidence interval for hazard ratio • P-value for treatment effect

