11.4. Secondary Efficacy Analyses

1. The effect of treatment on the iGFR at the end of the 3-year treatment period (before the washout) will be evaluated using the same analytical approach employed for the primary outcome.
2. The effect of treatment on the eGFR at 4 months after randomization will be evaluated using the same analytical approach employed for the primary outcome.
3. The iGFR and eGFR time trajectories, estimated from periodical iGFR measures and quarterly serum creatinine and cystatin C measurements using the CKD-EPI SCr and the CKD-EPI SCr-SCysC equations^{34,35}, respectively, will be analyzed using linear mixed-effects models.⁴⁰⁻⁴² The main objective of the analysis will be to construct confidence interval for the effect of the intervention over three years of observation (treatment main effect) and investigate whether the effect of the intervention changes with time (time by treatment interaction).
4. Time to serum creatinine doubling or ESRD in the two treatment groups is subject to censoring due to dropouts or reaching the end of study before the participant experiences the event. Survival time will be defined as the time from randomization to the event (the first of serum creatinine doubling from baseline or occurrence of ESRD, defined as eGFR \leq 15 ml/min/1.73 m², hemodialysis, or kidney transplant) or, for participants who did not experienced an event, to the last study visit. Data will be summarized by means of Kaplan-Meier survival curves and by providing the proportions of participants surviving without events at 1, 2, 3 years, and at the end of the wash-out period along with their 95% CIs. Given the potentially small number of events, differences between study groups will be tested by means of the log rang test or by means of simple Cox regression models including a limited number of predictors in addition to treatment group.
5. The effect of treatment on the AER at the end of the wash-out period, based on the geometric mean of two AER measured at this time point and adjusted for the geometric mean of AER at baseline (Visit 3 and 4), will be investigated in a linear regression model framework as in the case of the primary outcome.

6. The effect of treatment on the AER at the end of the treatment period, based on the geometric mean of the AER measures at visit 15 and 16 adjusted for the geometric mean of AER at baseline (Visit 3 and 4) will be investigated as in #5.

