3.6. Additional analysis assessing treatment effect on time to 40% eGFR decrease

RATIONALE:

Following internal discussion on the importance of the recently proposed measure of kidney decline, namely 40% eGFR decrease, we added this analysis.

PROTOCOL:

Not applicable

SAP:

Details are provided in SAP Section 6.8.5.

3.7. Additional analysis assessing time to doubling of serum creatinine, end-stage renal disease (ESRD), or cardiovascular/renal death

RATIONALE:

Following internal discussion on the importance of the recently proposed measure of kidney decline, namely using cardiovascular/renal death as part of the composite endpoint definition, we added this analysis.

PROTOCOL:

Not applicable

SAP:

Details are provided in SAP Section 6.8.6.

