No formal interim analyses of the primary endpoint will be conducted, therefore the nominal α level to be used at the final analysis will be 0.05 for the primary endpoint. All other secondary outcomes will also be tested at the 0.05 level, with no adjustment for multiplicity. Many of the models used in the analyses include baseline covariates, such as stratifying variables (serum uric acid (sUA), HbA1C, clinical site), iGFR, albuminuria status (subjects who qualified by ACR or AER or were albuminuric at baseline vs. subjects who qualified by eGFR slope and were normoalbuminuric at baseline), AER, and time, and time by treatment interaction. If there are problems with fitting these models, due, for example, to lack of convergence to optimal values, covariates will be eliminated from the models in the following order: baseline AER, albuminuria status, serum uric acid (sUA), HbA1c, and clinical site. More detailed information about these covariates is included in Section 6.4.

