6.4. Baseline covariates

The following is a description of the baseline covariates that will be used in the various analyses outlined in the remainder of Section 6.

- Stratifying variables
 - serum uric acid (sUA) at baseline with 2 levels (≤ 6.0 and > 6.0 mg/dl)
 - glycated hemoglobin (HbA1c) at baseline with two levels (≤ 7.8 and $> 7.8\%$)
 - clinical site/study center with 16 levels (based on main sites with satellite sites collapsed into main sites)
- Baseline iGFR measured at Visit 4
- Baseline eGFR measured at Visit 4
- Treatment group with two levels (Allopurinol, Placebo)
- Albuminuria status with 2 levels (subjects who qualified by ACR or AER or were albuminuric at baseline vs. subjects who qualified by eGFR slope and were normoalbuminuric at baseline)
- Baseline AER geometric mean (at Visits 3 and 4 combined) expressed on log to base 10 scale

As of Dec. 17, 2018, we have complete data available for baseline serum uric acid, treatment group, and study center. The number of missing values for the other baseline covariates is 1 for iGFR, 2 for HbA1c, and 17 for albuminuria status. Missing baseline data will be imputed according to the approach described in Section 6.5. When creating covariates for analytical and imputation purposes, we will aggregate clinical sites with a small number of randomized subjects, such as Edmonton (site #11, n=3) and Vancouver (site #16, n=11) will be combined with Calgary (site #10, n=20) in the same geographic region. Similarly, Spokane (site #15, n=5) will be combined with Seattle (site #13, n=35).

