6.7.5. Time to serum creatinine doubling or ESRD

Estimand	See section 5.2.5 for definition
Analysis Set	ITT Population
Methods	Proportional hazards model for interval censored data.
Dependent Variable	Time to composite endpoint of serum creatinine doubling or ESRD
Proportional Hazards Model	Fixed effects associated with: 
 • Stratifying variables: sUA, HbA1c, study center • Treatment group • Albuminuria status with 2 levels • Baseline AER geometric mean (at Visits 3 and 4 combined) expressed on log to base 10 scale • Baseline iGFR
Results	
 • N(%) of subjects with doubled serum creatinine or ESRD during the course of the study • Hazard ratio of allopurinol to placebo • 95% confidence interval for hazard ratio • P-value for treatment effect

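### The model for time to 40% eGFR decrease (SAP 6.8.5) is the only covariate-adjusted efficacy model in the current SAP without a baseline GFR term, and no reason is given.

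*SAP*

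**What the plan says.** SAP 6.8.5 fits a proportional hazards model for interval-censored data to "Time to endpoint of 40% eGFR decrease from randomization". Its covariates are the stratifying variables (serum uric acid, HbA1c, study center), treatment group, albuminuria status and, as the last line, "Baseline AER geometric mean (at Visits 3 and 4 combined) expressed on log to base 10 scale". The list stops there.

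SAP 6.7.5, for "Time to composite endpoint of serum creatinine doubling or ESRD", has the same lines and one more: "Baseline iGFR". So do 6.7.8 (cardiovascular events) and 6.8.6 (creatinine doubling, ESRD or cardiovascular/renal death).

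SAP 6.4 also defines "Baseline eGFR measured at Visit 4" as a covariate, and 6.7.3 and 6.7.4 use it for their eGFR outcomes.

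**The concern.** The endpoint is a percentage fall from each person's own eGFR. At a baseline of 40 it takes a loss of 16 ml/min/1.73 m²; at 90 it takes 36. If people lose GFR at a similar absolute rate, those who start low reach the threshold far more often, and baseline GFR is then a covariate one would want in the model. It is odd to find it missing from this model alone.

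Two things are at stake, both modest. One is a small loss of precision in an analysis likely to have few events. The other is pre-specification: if someone notices the gap after unblinding, adding the term then becomes a data-dependent choice.

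**Working it through.** **1. Covariate lists compared (current SAP)**

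| Model | Baseline GFR term |
|---|---|
| 6.6.1 primary; 6.7.1 (same fit); 6.6.2 ANCOVA (same covariates) | iGFR |
| 6.7.2 iGFR trajectory | iGFR |
| 6.7.3 eGFR at 4 months; 6.7.4 eGFR trajectory | eGFR |
| 6.7.5 creatinine doubling or ESRD | iGFR |
| 6.7.6 and 6.7.7 AER | iGFR |
| 6.7.8 cardiovascular events | iGFR |
| 6.8.1 subgroups; 6.8.4 uric acid change | iGFR |
| **6.8.5 40% eGFR decrease** | **none** |
| 6.8.6 doubling, ESRD or cardiovascular/renal death | iGFR |

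Time to first SAE (6.8.2) uses Kaplan-Meier methods without covariates, so it is not part of the comparison.

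**2. Is a reason given?** SAP 3.6 says only: "Following internal discussion on the importance of the recently proposed measure of kidney decline, namely 40% eGFR decrease, we added this analysis". The fallback in SAP Section 6 for models that do not fit reads "covariates will be eliminated from the models in the following order: baseline AER, albuminuria status, serum uric acid (sUA), HbA1c, and clinical site"; baseline GFR is not on that list.

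**3. Planning inputs (Protocol 11.10).** Difference 3, residual SD 10.1, two-sided alpha 0.05, power 80%: n per group = 2 × (1.960 + 0.842)² × (10.1/3)² ≈ 178, against the stated 180. The inputs reproduce. The documents give no event count or power for 6.8.5.

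**4. How prognostic would baseline GFR be?** Take the untreated loss of 3 per year, 9 over 3 years, SD 10.1, and the entry eGFR range 40 to 99.9. For baseline b, the event is a 3-year value at or below 0.6b.

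(a) Same absolute loss at every baseline: P = Φ[(0.6b − (b − 9))/10.1].
- b = 40: Φ[(24 − 31)/10.1] = 24.4%
- b = 50: Φ[(30 − 41)/10.1] = 13.8%
- b = 70: Φ[(42 − 61)/10.1] = 3.0%
- b = 99.9: Φ[(59.94 − 90.9)/10.1] = 0.1%

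(b) Regression to the mean. Protocol 11.10 equates 10% of residual variance with 4% of total variance, so residual variance is 40% of the total and baseline explains 60%. With slope √0.6 and an assumed mean baseline of 70: 8.7% at 40, 3.0% at 70, 0.8% at 99.9. With an assumed mean of 65 the range is 10.6% to 1.1%; with 75 it is 7.0% to 0.6%.

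(c) Loss and SD proportional to baseline, scaled to match at 70: Φ[(0.6 − (1 − 9/70))/(10.1/70)] = 3.0% at every baseline.

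**5. What would adjustment change?** Simulations with 530 participants and losses of 3 versus 2 per year. Assumed: baseline mean 70, SD 16, truncated to 40 to 99.9.

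Event status at 3 years only, about 1,500 trials per scenario, 12 to 20 events, with treatment and, when adjusted, baseline eGFR as the only covariates:

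| Scenario | Treatment HR without / with baseline eGFR | Power without / with |
|---|---|---|
| (a) | 0.540 / 0.541 | 21.8% / 23.7% |
| (b) | 0.496 / 0.493 | 16.4% / 16.7% |
| (c) | 0.496 / 0.489 | 13.5% / 13.7% |

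Events detected over the repeated visit schedule:
- Absolute loss, slope SD 3 to 5, visit noise SD 4 to 6 (400 trials per scenario): HR per SD of baseline eGFR 0.32 to 0.54; treatment z 3 to 6% larger; power up 1 to 7 points. Under proportional loss there was no gain.
- Slope SD 3.4 or 4.5, eGFR noise 5% or 10% (150 trials per scenario): under absolute loss, HR per SD 0.46 to 0.56 with 5% noise but 0.85 to 0.86 with 10% noise; under proportional loss, 1.08 to 1.48. Across all eight scenarios z changed by −0.6% to +3.0%.

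Information scales with z², so a 6% larger z is worth about 1.06² − 1 = 12% more events. At the low power in play that is little: moving z from 1.32 to 1.39 raises power from Φ(1.32 − 1.96) = 26% to Φ(1.39 − 1.96) = 28%.

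**The case against.** The strongest reply is that nothing here is biased and little is lost. Treatment was randomized, so the comparison is valid without baseline GFR. The analysis sits under SAP 6.8 (Other analyses), neither primary nor secondary. The endpoint is already scaled to each person's baseline, and measurement noise works against adjustment: a baseline reading that is high by chance makes an apparent 40% fall more likely, which weakens the association. All of this stands, and it is why the point is small.

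A second reply is parsimony. For creatinine doubling or ESRD, Protocol 11.4 allowed "simple Cox regression models including a limited number of predictors in addition to treatment group", because events may be few. That is a reason to keep event models small, but it does not explain this omission: 6.8.5 keeps study center (16 levels before small sites are combined) and every other covariate.

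A reader might infer that baseline GFR is one of the strongest predictors of this event. The documents rank no predictors, and the inference depends on absolute loss not varying with baseline. A reader might also infer that the omission makes the result incomparable with 6.7.5 and 6.8.6. Those models use iGFR and count different events, so adding eGFR would not match them exactly either.

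**Conclusion.** The omission is plain in the text, unique among the SAP's covariate-adjusted efficacy models, and unexplained. It looks like a dropped line. Baseline GFR would be clearly prognostic under the plan's constant-loss assumption applied at every baseline, and much less so or not at all under proportional loss.

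The expected gain is a treatment z about 0 to 6% larger. The upper end needs absolute loss and modest measurement noise. It should not be read as a certain saving of a tenth of the events, nor as a hazard ratio distorted by bias: the models with and without the term estimate slightly different hazard ratios, and both comparisons are valid. The simulations rest on assumed baseline, slope and noise distributions that the documents do not give. In the 3-year-only runs, AER and the other covariates already in 6.8.5 were left out; they could absorb part of any gain.

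This is a free improvement, not a threat to the trial's conclusions.

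**What to change.** Add baseline eGFR at Visit 4 to the covariates in SAP 6.8.5, before unblinding. It is preferable to iGFR here because it is the natural reference for the 40% fall and is the term the SAP already uses for its eGFR outcomes in 6.7.3 and 6.7.4. Compute it with the same equation as the endpoint. If the omission is deliberate, say why in 3.6 or 6.8.5.

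The cost is one line of text and one model term, with no new data. If unblinding has already happened, keep the model as written and report the adjusted fit as a labelled sensitivity analysis.

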2. STUDY OBJECTIVE

To determine whether lowering serum UA by means of oral allopurinol is effective in preventing or slowing decline of renal function in T1D patients with microalbuminuria or moderate macroalbuminuria who still have only mildly or moderately impaired kidney function.

3. STUDY DESIGN

The study will be a multi-center, double-blind, placebo-controlled, parallel-group randomized clinical trial including a total of 480 patients with type 1 diabetes (T1D) who are at high risk for GFR loss because of increased albuminuria and a relatively high serum UA (≥ 4.5 mg/dl), but have only mildly or moderately decreased renal function.

7. STUDY OUTCOMES

7.1. Primary outcome

The primary outcome will be the iGFR at the end of the 2-month wash-out period following the 3-year treatment period, measured by the plasma clearance of non-radioactive iohexol (iGFR) and adjusted for the iGFR at baseline. The rationale of measuring the primary outcome at the end of the wash-out period is to test allopurinol for permanent effects of on the natural history of kidney disease, independent from any transient, hemodynamic effect that the medication may have on GFR. Plasma iohexol clearance has been shown to provide accurate and reproducible GFR measurements.^{30,31} It is highly correlated with inulin clearance (the gold standard to measuring GFR)³² and is a safe, cost-effective method to test hundreds of patients enrolled in multicenter clinical trials.³³ The method consists of injecting a 5 mL bolus of Iohexol (Omnipaque, 300 mg iodine/mL) and drawing blood samples at baseline and 120, 150, 180, 210, and 240 minutes after the injection. Plasma concentrations of iohexol at different time points are measured by HPLC and used to calculate the plasma clearance of iohexol ($Cl = \text{Dose}/\text{AUC}$, where AUC is the area under the plasma concentration time curve), which is taken after appropriate body surface area corrections as a measure of GFR.^{30,31}

7.2. Secondary outcomes

1. Iohexol-clearance GFR at the end of the 3-year treatment period (before the washout).
2. Iohexol-clearance GFR time trajectory estimated from periodical iohexol-GFR measurements.
3. Estimated (eGFR) at 4 months estimated from serum creatinine and cystatin C and adjusted for the eGFR at baseline.
4. Estimated GFR (eGFR) time trajectory estimated from quarterly serum creatinine and cystatin C measurements using the CKD-EPI SCr and the CKD-EPI SCr-SCysC equations.^{34,35}
5. Time to doubling of baseline serum creatinine value or ESRD (eGFR ≤ 15 ml/min/1.73 m², institution of dialysis, kidney transplantation).
6. Geometric mean of two AER measurements at the end of the 2-month wash-out period following the 3-year treatment period, adjusted for the mean urinary AER at baseline. Urinary AER will be determined in timed overnight urine collections brought by study participants to regular clinic visits, and expressed in $\mu\text{g}/\text{minute}$ and as urinary albumin/creatinine ratios.
7. Geometric mean of urinary AER during the last three months of the treatment period (Visits 15 and 16), adjusted for the mean urinary AER at baseline.
8. Time to fatal or non-fatal cardiovascular events, defined as the composite of CVD death (ICD-10 code I10 to I74.9), myocardial infarction, stroke (ischemic or hemorrhagic), coronary artery bypass grafting, or percutaneous coronary intervention.

Figure 1. Schedule of events

Year	1	1	1	1	1	1	1	1	1	1	2	2	2	3	3	3	3	3
Week	-12	-9	-7	-3		0	4	16	32	48	64	80	96	112	128	142	156	164
Visit #	1	2	3	4	4a*	5	6	7	8	9	10	11	12	13	14	15	16	17
Type of Visit: In-Person Visit Required (V); Phone Call (C); Other Visit (In-Person or Remote Visit, O)	O	V	O	V	V	C	O	O	O	O	O	V	O	O	O	O	V	V
EVENT	Screen	Run-in				RANDO 100 mg	Allopurinol or placebo										Wash-out	
		200-400 mg										EOS						
Informed Consent	x	x																
Demographics	x																	
Initial Medical Hx		x																
Interval Medical Hx and BP Control			x	x	(x)		x	x	x	x	x	x	x	x	x	x	x	x
Concomitant Meds	x	x	x	x	(x)		x	x	x	x	x	x	x	x	x	x	x	x
Blood Pressure and Measurements	x	x	(x)	x	(x)		(x)	(x)	(x)	(x)	(x)	x	(x)	(x)	(x)	(x)	x	x
ECG Report		x		x	(x)							x					x	
Physical Exam		x		(x)	(x)							x					x	
Skin Assessment				x	(x)		x	x	x	x	x	x	x	x	x	x	x	x
Eligibility	x			x	(x)	x												
Randomization						x												
Family History				x	(x)													
RAS and BP Med Log		x	x	x	(x)		x	x	x	x	x	x	x	x	x	x	x	x
IGFR Procedure				x	(x)						x						x	x
PERL Study Drug Prescription						x	x	x	x	x	x	x	x	x	x	x	x	
Study Drug Compliance							x	x	x	x	x	x	x	x	x	x	x	
CENTRAL LAB																		
Serum uric acid, serum creat, cystatin C	x		x	x	(x)		x	x	x	x	x	x	x	x	x	x	x	x
Urine ACR/AER	x		x	x	(x)			x	x	x	x	x	x	x	x	x	x	x
HbA1c	x			x	(x)			x	x	x	x	x	x	x	x	x	x	x
HLA B*58:01				x	(x)													
iGFR				x	(x)							x					x	x
NIDDK Repository: serum, plasma, urine				x								x					x	x
LOCAL LAB																		
Pregnancy test serum HCG	x		x	x	(x)		x	x	x	x	x	x	x	x	x	x	x	x
Pregnancy test urine dipstick		x		x	(x)						x						x	x
ALT, K, CBC, serum creatinine, urine	x		x	x	(x)		x	x	x	x	x	x	x	x	x	x	x	x
Protocol Deviation		x	x	x	(x)		x	x	x	x	x	x	x	x	x	x	x	x
Adverse Events		x	x	x	(x)	x	x	x	x	x	x	x	x	x	x	x	x	x

*If normal blood pressure control is not achieved at Visit 4, the run-in period may be extended for two more weeks after which participants will be examined as in Visit 4 (Visit 4A). In this event, the GFR measurement scheduled for Visit 4 will be conducted at Visit 4A.

^ Study visits will be generally conducted at the Study Sites or their Satellites. "In-Person Visits" (V) are required for Visit 2 and all visits requiring iohexol-GFR measurements. If a participant lives far from a study site or satellite, or travel impediments are present, other (O) visits may be conducted remotely or in-person. For any given study visit to be conducted remotely, a Phone Visit and a Remote Biospecimen Collection will be both required; a Phone Visit is performed by the study coordinator using the telephone or other media such as Skype to collect results of study procedures that do not require physical interactions (e.g., collection of medical history), and a Remote Biospecimen Collection is performed at a clinical laboratory close to where participants live.

Note: (x) indicates an optional assessment; For "BP and Measurements", (x) indicates an optional assessment only if the patient is NOT seen in-person.

